**Remarks:**

1. Events can only be combined into one and the same AE if their start and stop dates are known.
2. In case the completely missing end date is imputed (for period allocation), this date is also considered as a complete date.

## 3. Time is not considered when determining overlap of events.

The AESIs will be presented by phase as well as by time interval. The definition of the different time intervals can be found below. Attribution to the intervals will be done similarly to the unsolicited AEs as described above. For Step 2 of phase allocation of adverse events, the '0 - 28 days post-dose' intervals should be treated similar to 'active' periods and the rest as 'non-active' periods.

The definition of the time intervals is shown in the table below. Additionally, in the tables a '0-56 days post-dose' interval and a '0-6 months post-dose' interval should also be shown. The '0-56 days post-dose' interval is the combination of the '0 - 28 days post-dose' interval and the '29 - 56 days post-dose' interval. The '0-6 months post-dose' interval is the combination of the '0 - 28 days post-dose', '29 - 56 days post-dose' and '57 days - 6 months post-dose' intervals.

**Definition of intervals:**

Dose	Interval	From	to
Post-vaccination 1	0-28 days post dose	Date time of the 1 st vaccination	Min of: 
 
23:59 at the date of last contact (for discontinuations)
 
23:59 at date of DB cut-off for interim analyses
 
Maximum(Date of Vaccination 1 + 28 days at 23:59, date of scheduled visit 4 weeks after 1st vaccination at 23:59)
 

	29-56 days post dose	One minute after the end of the interval 0-28 days post dose	Min of: 
 
23:59 at date of last contact (for discontinuations)
 
23:59 at date of DB cut-off for interim analyses
 
Date of Vaccination 1 + 56 days at 23:59
 

	57 days - 6 months post-dose	One minute after the end of the interval 29-56 days post dose	Min of: 
 
23:59 at date of last contact (for discontinuations)
 
23:59 at date of DB cut-off for interim analyses
 
Maximum of (Date of Vaccination 1 + 183 days at 23:59, date of scheduled visit 183 days post 1st vaccination at 23:59)
 

	>6 months post-dose	One minute after the end of the interval 57 days - 6 months post-dose	Min of: 
 
23:59 at the date of last contact (for discontinuations)
 
23:59 at the date of DB cut-off for interim analyses
 

			
 
1 min prior to date time of vaccination 2
 

Post-vaccination 2	0-28 days post dose	Date time of the 2nd vaccination	Min of: 
 
23:59 at the date of last contact (for discontinuations)
 
23:59 at date of DB cut-off for interim analyses
 
Maximum(Date of Vaccination 2 + 28 days at 23:59, date of scheduled visit 4 weeks after 2nd vaccination at 23:59)
 

	29-56 days post dose	One minute after the end of the interval 0-28 days post dose	Min of: 
 
23:59 at date of last contact (for discontinuations)
 
23:59 at date of DB cut-off for interim analyses
 
Date of Vaccination 2 + 56 days at 23:59
 

	57 days - 6 months post-dose	One minute after the end of the interval 29-56 days post dose	Min of: 
 
23:59 at date of last contact (for discontinuations)
 
23:59 at date of DB cut-off for interim analyses
 
Maximum (Date of Vaccination 2 + 183 days at 23:59, day 547 visit at 23:59)
 

	>6 months post-dose	One minute after the end of the interval 57 days - 6 months post-dose	Min of: 
 
23:59 at the date of last contact (for discontinuations)
 
23:59 at the date of DB cut-off for interim analyses
 

The combination of the '0 - 28 days post-dose' interval and the '29 - 56 days post-dose' interval will be referred as '0 - 56 days post-dose'.

The combination of the '0 - 28 days post-dose', '29 - 56 days post-dose' and '57 days - 6 months post-dose' intervals will be referred as '0-6 months post-dose'.

#### 5.3.2.4. Missing Data

Missing data will not be imputed. Participants who do not report an event will be considered as participants without an event. An AE with a missing severity or relationship will be considered as an AE reported but will be considered as not reported for the severity or relationship. For example, an AE with missing severity will be considered as an AE reported for the analysis of any grade but will be considered as not reported for the analysis of at least grade 3.

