## 6.9. Study Pausing Rules

For Cohort 1, randomization and vaccination of participants will be suspended during review of the 24-hour data following the first administration of study vaccine to sentinel participants in each group (see Section 4.1).

If a study vaccination is considered to raise significant safety concerns (and a specific set of pausing criteria have been met), further vaccination of participants will be paused. The concerned data will be reviewed by the DRC, after which the DRC will recommend whether the pause can be lifted or not, or whether other steps are needed.

---

a Note: Ocular, topical, intra-articular or inhaled steroids are allowed.

The DRC will review blinded data first but has the right to request the randomization codes and review unblinded data if deemed necessary. The DRC will make recommendations regarding the continuation of the study to the sponsor study team. The sponsor study team will communicate conclusions regarding study continuation to the investigator, the Independent Ethics Committee (IEC) / Institutional Review Board (IRB), and applicable health authorities as appropriate.

After the first DRC meeting triggered by the occurrence of a given pausing rule, the DRC will convene thereafter for each additional participant meeting that pausing rule.

The occurrence of any of the following events will lead to a pause in further study vaccination. This list is only applicable for concerned AEs that occur up to 4 weeks after each vaccination and to concerned SAEs and AESIs.

1. Death of a participant, considered related to study vaccine or if the causal relationship to the study vaccine cannot be excluded; OR

Note: All cases of death will be sent for DRC information. Upon their review, DRC may then decide whether a study pause is required.

2. One or more participants per cohort experience an SAE, AESI (ie, confirmed TTS), or a Grade 4 (solicited or unsolicited) adverse event or a persistent (upon repeat testing) Grade 4 laboratory abnormality that is determined to be related to study vaccine (in Cohorts 1 and 2 only); OR
3. One or more participants per cohort experience anaphylaxis or generalized urticaria within 24 hours of vaccination, clearly not attributable to other causes than vaccination with study vaccine; OR

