### 9.2.3. Expanded Safety Cohort (Cohort 3)

The expanded safety cohort (Cohort 3) should provide sufficient safety data on the selected vaccine formulation to support late-stage development if the immunogenicity results of Cohort 2 are satisfactory.

Table 15 shows the probabilities of observing at least one AE in the expanded safety cohort with 150 participants per vaccine formulation, 50 participants receiving placebo, and 50 participants receiving  $1 \times 10^{11}$  vp Ad26.RSV-A.preF/ 150 µg RSV-A preF protein, at given true AE rates. This table shows that the current numbers give a reasonable probability to also observe less frequent events in the active arms in this cohort. Combining the 60 participants from Cohorts 1 and 2 and 150 participants from Cohort 3 for the selected vaccine formulation results in 210 participants for this formulation.

**Table 15: Probability of Observing at Least One Adverse Event in the Expanded Safety Cohort (Cohort 3) at a Given True Adverse Event Rate**

| True AE Rate (%) | Probability of Observing at Least One AE in N Participants (%) |        |        |        |
|------------------|----------------------------------------------------------------|--------|--------|--------|
|                  | N=50                                                           | N=60   | N=150  | N=210  |
| 0.5              | 22.2%                                                          | 26.0%  | 52.9%  | 65.1%  |
| 1                | 39.5%                                                          | 45.3%  | 77.9%  | 87.9%  |
| 2.5              | 71.8%                                                          | 78.1%  | 97.8%  | 99.5%  |
| 10               | 99.5%                                                          | 99.8%  | 100.0% | 100.0% |
| 25               | 100.0%                                                         | 100.0% | 100.0% | 100.0% |
| 50               | 100.0%                                                         | 100.0% | 100.0% | 100.0% |

AE = adverse event; N = number of participants.

The observation of 0 events (eg, SAEs) is associated with 95% confidence that the true event rate is below the rates specified in Table 16 for the considered number of participants.

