#### 5.3.2. Analysis Methods for the Primary Safety endpoints

No formal statistical testing of safety data is planned. Safety data will be analyzed descriptively by cohort (or pooled over cohorts, as applicable) and study arm, and by group (cohort 1), as applicable, per phase and across the entire study period. All safety analyses will be made on the FAS.

The verbatim terms used in the eCRF by investigators to identify AEs will be coded using the Medical Dictionary for Regulatory Activities (MedDRA). Any AE occurring at or after the first vaccination is considered to be treatment emergent. All reported AEs with onset during the active phase (ie, AEs occurring after vaccination up to 28 days post-vaccination) or AEs present before the active phase but worsening during the active phase, and all SAEs, AEs leading to study or vaccine discontinuation during the study, potential AESIs and AESIs (up to 6 months after vaccination) will be included in the analysis. For each AE, the percentage of participants who experience at least 1 occurrence of the given event will be summarized. All other unsolicited adverse events collected outside the 28-day period will be presented through listings.

AESIs (as determined in Section 5.3.2.1) will be reported until 6 months post vaccination and additionally by different time periods:

- 0 – 28 days post dose,
- 29 days – 56 days post dose,
- 0 – 56 days post dose,
- 57 days – 6 months post dose,
- 0 – 6 months post-dose.

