### **5.3.2.2. Analysis of Adverse Events**

Number and percentage of participants with at least one particular AE (unsolicited/solicited) will be tabulated. Unsolicited AEs will be summarized by System Organ Class (SOC) and Preferred Term (PT).

Solicited AEs will be summarized by class (administration site, systemic) and Derived Term. The number and percentages of participants with at least one solicited local (at injection site) or systemic adverse event will be presented. For solicited AEs, the following tables will be provided: overall summary, by worst severity grade, at least grade 3, related (systemic only), time to onset (in days) and duration (in days). Note: Duration is defined as number of days from the start of the event until resolution of the event. The time to first onset is defined as date of first onset – reference date + 1. The reference date is the start date of the post-dose period. For solicited AEs, the denominator for the percentages is the number of participants with solicited event data assessed by the investigator in the considered population, phase and arm (incidence per 100 participants/phase).

A tabulation of the distribution of temperatures per half degree intervals will also be provided.

Frequencies of unsolicited AEs, separately for all and vaccination-related only, will be presented by SOC and PT. The following tables will be provided: overall summary, all AEs, most frequent AEs, AEs with at least grade 3, related AEs, AEs leading to death, AEs leading to study discontinuation, SAEs, related SAEs, potential AESIs and AESIs, COVID-19 related AEs.

AESIs, AEs flagged by the investigator as potential AESI and AESIs identified via a programmed selection will be summarized by Interest Category and PT. Denominator for the percentages is the number of participants in the considered population, phase and arm (incidence per 100 participants/phase).

Potential AESIs selected programmatically will be tabulated by categories: ‘Embolic and thrombotic events (SMQ)’ and ‘Haematopoietic Thrombocytopenias (SMQ) (broad) or HLT = Thrombocytopenias’. Potential AESI determined programmatically, related to study vaccine (investigator assessment), will be tabulated similarly.

Potential AESIs as identified by the investigator, will be tabulated by categories: ‘Embolic and thrombotic events (SMQ)’ and ‘Haematopoietic Thrombocytopenias (SMQ) (broad) or HLT =

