### **5.7.2. Vital Signs**

Vital signs including temperature, heart rate, respiratory rate, and blood pressure (systolic and diastolic) will be summarized over time, using descriptive statistics and/or graphical representations. The percentage of participants with values beyond clinically important limits will be summarized. Baseline and emerging vital sign abnormalities will be listed based on the abnormality gradings in Appendix 6 of the CTP. An abnormality will be considered as emerging if it is worse than the baseline value. If the baseline is missing, the abnormality is always considered emerging.

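### AEs with missing severity or relationship drop out of the Grade 3 or higher and related tables while the denominator stays the same, and no count or worst-case table shows how many were dropped

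*SAP*

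**What the plan says.** SAP 5.3.2.4 opens with "Missing data will not be imputed". It then says that an AE with missing severity or relationship "will be considered as an AE reported but will be considered as not reported for the severity or relationship". The SAP's own example is an AE with no grade, which counts in the any-grade analysis but "will be considered as not reported for the analysis of at least grade 3".

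The outputs affected are listed in SAP 5.3.2.2. For unsolicited AEs the list includes "AEs with at least grade 3, related AEs, AEs leading to death, AEs leading to study discontinuation, SAEs, related SAEs". For solicited AEs it includes an at-least-Grade-3 table and, for systemic events only, a related table.

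Under SAP 5.3.2 the measure is at participant level: "the percentage of participants who experience at least 1 occurrence of the given event will be summarized". SAP 5.3.2.2 takes the denominator for solicited AEs as the participants with investigator-assessed solicited data. In its paragraph on AEs of special interest it takes the participants in the population, phase and arm. Nothing there removes a participant because an event lacks a grade or a causality judgement.

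Neither document plans a count of AEs with missing severity or relationship, or a table that treats them as qualifying.

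**The concern.** An event of unknown causality contributes nothing to the related tables, and an event of unknown grade contributes nothing to the Grade 3 or higher tables, yet the participant still counts in the denominator. In those tables the participant looks the same as one with no qualifying event. Nothing in the planned outputs tells the reader how often this happened.

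Safety is a primary endpoint in Cohorts 1 to 3 (SAP 5.3.1), and the study is first-in-human for the RSV-B components (Protocol 2). Arms in Cohorts 1 and 2 combined have about 60 participants (12 + 48 in most arms), so one participant moves a rate by 1/60 = 1.7 percentage points. Protocol 9.2.3 also relies on zero-event reasoning: "The observation of 0 events (eg, SAEs) is associated with 95% confidence that the true event rate is below the rates specified". For a table that depends on grade or causality, a zero is only as reassuring as the completeness of that field.

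**Working it through.** **1. Direction within an arm.** Take an arm with n participants. Let X be the number with at least one event that would qualify if every field were filled in, and Y the number tabulated under the SAP rule. The rule removes events from the numerator and adds none, so Y ≤ X. The denominator n is unchanged, so Y/n ≤ X/n. Equality holds when nothing is missing, when the missing value would not have qualified, or when the participant has another qualifying event in the same table.

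**2. Which events are exposed.**
- *Relationship, solicited local AEs:* not exposed, because they are related by definition (SAP 5.3.2.1; Protocol 10.4.2).
- *Relationship, solicited systemic and unsolicited AEs:* exposed.
- *Severity, solicited AEs:* largely protected. A diary symptom becomes a solicited AE only once it is Grade 1 or above (Protocol 8.3.2), and grades for erythema, swelling and fever are derived from measurements (Protocol 10.4.3).
- *Severity, unsolicited AEs:* exposed.
- *All-AE, SAE and death tables:* not affected, since none depends on grade or causality.

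**3. The plan's own figures.** Table 16 uses 1 − 0.05^(1/n). This gives 4.87% for n = 60 (stated 4.9%) and 1.98% for n = 150 (stated 2.0%). Table 15 uses 1 − (1 − p)^n. For n = 150 and p = 0.5% this gives 52.85% (stated 52.9%). All reproduce.

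**4. One dropped participant.** This assumes that the event truly qualifies and is the only one in the arm. The exact one-sided 95% upper limits are:

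| n | 0 tabulated | 1 if complete |
|---|---|---|
| 60 | 4.87% | 7.66% |
| 150 | 1.98% | 3.12% |

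Table 16 gives SAEs as its example, and the overall SAE table does not change under this rule. Applying the arithmetic to related or Grade 3 or higher events is an illustration.

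**5. A range of missingness.** Suppose a share m of participants with a qualifying event have it recorded only with the field blank. The tabulated rate is then p(1 − m). The chance of at least one tabulated event is 1 − (1 − p(1 − m))^150, and the zero-event limit on the true rate is 1.98%/(1 − m). With p = 0.5%, n = 150 and assumed values of m:

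| m | Chance of ≥1 tabulated | Zero-event limit |
|---|---|---|
| 0 | 52.9% | 1.98% |
| 2% | 52.1% | 2.02% |
| 5% | 51.0% | 2.08% |
| 10% | 49.2% | 2.20% |
| 20% | 45.2% | 2.47% |

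**6. Main table against worst case.** Assume 150 participants, 12 with a known Grade 3 or higher AE and k more whose only candidate AE has no grade. The SAP rule gives 12/150 = 8.0% for any k. The worst case gives (12 + k)/150, which is 8.7% for k = 1, 10.0% for k = 3 and 11.3% for k = 5. The complete-data rate lies between the two figures.

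**7. Between arms.** Assume 12/150 on active vaccine and 4/50 on placebo, both 8.0%. If one placebo event lacks a grade, the tables show 8.0% against 3/50 = 6.0%. The vaccine then looks 2.0 points worse although the complete data show no difference.

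**The case against.** The strongest reply is that the problem should hardly arise. Investigators must record an opinion on relationship (Protocol 10.4.5), and all AEs are coded for severity (Protocol 10.4.3). SAE forms are reviewed by a site physician and sent within 24 hours (Protocol 8.3.1), and queries are raised in the data-capture tool (Protocol 10.3.9). No formal safety testing is planned. Counting every blank as related in the main tables would only replace one one-sided rule with another. This stands. It limits the likely size and is a good reason to leave the main tables alone, but it does not give the reader a way to see whether any events were dropped.

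Several stronger readings are tempting but not supported:
- *The SAP recodes blanks as not related or below Grade 3.* It says not reported for that attribute. In Protocol 10.4.2, not related is a positive judgement by the investigator. Only the effect on the numerator is the same.
- *Gaps in the data always flatter the vaccine.* Steps 1 and 7 show otherwise. A completely missing start date also works the other way: SAP 5.3.2.3 puts the event in the post-dose period unless its end date is earlier.
- *The rule contradicts the rest of the plan.* SAP 5.7.2 says "If the baseline is missing, the abnormality is always considered emerging", but that rule and the start-date rule concern emergence and timing. The pausing rule in Protocol 6.9 covers "Death of a participant, considered related to study vaccine or if the causal relationship to the study vaccine cannot be excluded", which describes an assessment someone has made and governs vaccination pauses, not tables.
- *A death with blank causality would disappear.* It would be absent from the related tables but present in the SAE and death tables, and Protocol 6.9 sends all deaths to the Data Review Committee.
- *Many fields will be open at the formulation-selection analysis.* The documents give no interval between the last Day 29 visit and database lock, and no specific role for these rates in selection.

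**Conclusion.** The point holds in limited form. SAP 5.3.2.4 is a stated rule that can only understate the Grade 3 or higher and related rates within an arm or leave them unchanged. Neither a count of missing values nor a worst-case table is planned to show how much.

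The size is unknown because no missing rate is given, and it is probably small because causality entry is mandatory. With nothing missing, the tables are exactly right. The percentages in steps 4 to 7 rest on assumed counts or shares and show scale only. The direction of any effect on comparisons between arms is not fixed. This is a cheap improvement to the reporting of primary safety endpoints in a first-in-human study. It is not evidence that the planned tables will mislead.

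**What to change.** Add two provisions to SAP 5.3.2.4:

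1. Footnote the at-least-Grade-3, related-AE and related-SAE tables with the number of AEs and of participants, by arm, that have missing severity or missing relationship.
2. Add a worst-case version of those tables that counts missing relationship as related and missing severity as at least Grade 3, applied identically to every arm including placebo.

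The main tables may stay as planned. Read together, the two versions bracket the rate that complete data would give. If the footnote count is zero, they coincide.

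The cost is two sentences in the SAP, a programming flag and a few extra outputs. The worst-case percentages may be slightly less favourable than the main ones.

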#### 5.3.3. Analysis Methods for the Primary Immunogenicity endpoint(s)

For Cohort 1, 2 and 4 the primary endpoint will be RSV neutralization antibody titers measured for RSV-A and RSV-B. In Cohort 3, RSV neutralization antibody titers are a secondary endpoint.

Data of corresponding arms from Cohort 1 and Cohort 2 will be combined in all analyses. Immunogenicity data of corresponding arms from Cohort 3 and Cohort 4 will be combined as applicable, too.

Descriptive statistics will be used for all arms to analyze the actual values (geometric mean, 95% CI, minimum, maximum, median and quartiles) and fold increase from baseline at all timepoints, as well as the percentage of participants with 2- and 4-fold increases from baseline. Additionally, the RSV-A/RSV-B antibody ratio will be reported by time points and the fold increase of RSV-A/RSV-B antibody ratio from baselines will be calculated at all timepoints.

For combined data from Cohort 1 and Cohort 2, geometric mean ratios for each active arm relatively to control Arm 1a and relatively to control Arm 1b, as well as relatively to each other will be calculated at all available timepoints along with corresponding 95% CI as applicable.

For Cohort 3, Arms 11a and 11b will be combined and the active arms (10, 11a+11b, 13) will be compared to each other at all available timepoints up to 1 year after vaccination on Day 1 by calculating the geometric mean ratios along with corresponding 95% CIs.

For durability and revaccination evaluation analyses, the following arms will be combined and compared to each other for all timepoints:

- Arm 11a (Cohort 3) combined with Arm 14 (Cohort 4);
- Arm 11b (Cohort 3) combined with Arm 15 (Cohort 4);
- Arm 12 (Cohort 3) combined with Arm 16 (Cohort 4).

Geometric means per arm of values for RSV-A, RSV-B and the ratio of RSV-A/RSV-B, geometric mean ratios for RSV-A, RSV-B and the ratio of RSV-A/RSV-B between all active arms along with corresponding 95% CIs will be estimated via an analysis of variance (ANOVA) using log-transformed post-vaccination immuno parameter response as dependent variable and study arm as independent variable. The means and differences in mean and CIs will be back transformed (by exponentiation) to CIs around a geometric mean or geometric mean ratio. This analysis will be performed by time points, separately per parameter. As a sensitivity analysis, the ANOVA may also be performed adjusting for baseline titer, age and sex.

Graphical presentation of actual values, fold increase from baseline and geometric mean ratios (between active arms) will be presented in scatterplots, boxplots, dot-plots, spaghetti plots etc. as applicable. In addition, plots of geometric mean titers (GMT) over time, combining the regimens in one graph (without individual participant dots) will be created. Reverse distribution curves of the actual values will be provided, for baseline and the different timepoints. In the graphs, original values will be displayed on the log2 scale.

